COVID-IVIG Protocol Cover Page

Study Title: Randomized Open Label Study of Standard of Care Plus Intravenous Immunoglobulin(IVIG) Compared to Standard of Care Alone in the Treatment of COVID-19 Infection

NCT Number: NCT04411667

Document Date: 19May2020

Protocol name: COVID-IVIG

Principal Investigator: [name]; [contact]; [contact]
IRB # 2004902

Title: Randomized Open Label Study of Standard of Care Plus Intravenous Immunoglobulin (IVIG) Compared to Standard of Care Alone in the Treatment of COVID-19 Infection

Primary Objective:

1. To identify whether or not IVIG can halt the progression to respiratory failure requiring mechanical ventilation in subjects admitted to the hospital with confirmed COVID-19.

Secondary Objectives:

1. To identify whether adding IVIG to the standard of care will reduce days requiring oxygen therapy.
2. To identify whether adding IVIG to the standard of care will reduce total hospital days.

Hypothesis: We hypothesize that the addition of IVIG will be beneficial in abating acute lung injury in subjects with SARSCoV-2 induced hypoxia that results in organ injury in such patients.

Background: Coronaviruses has been known zoonotic pathogens since the early 1970's. Bats have been identified as the main natural reservoir and domesticated animal intermediary species (e.g., camels, cats) have facilitated transmission to humans. In late 2019, a novel coronavirus (SARS-CoV-2) emerged in humans, originating in Wuhan, China and spreading across the globe as a pandemic, causing coronavirus disease of 2019 (COVID-19).

The current mortality rate (17MAR2020) is not well described because of the shortage of laboratory testing assays worldwide. Using WHO data on the cumulative number of deaths to March 1, 2020, mortality rates would be 5.6% (95% CI 5.4–5.8) for China and 15.2% (12.5–17.9) outside of China⁸.

Grave concerns are raised about the ability of the US healthcare system to handle the demand of subjects affected by the COVID-19 pandemic. While 80-85% of identified COVID-19 patients are asymptomatic or have mild disease, the 15-20% of patients requiring medical support (of which 1/3-1/2 are estimated to require ICU care) would pose dire consequences of healthcare access with current resources. Therefore, while the spread of virus continues to escalate, the ability to abort subjects away from the path of acute lung injury requiring mechanical ventilation would render an extreme advantage to healthcare systems. The average time from hypoxia to mechanical ventilation is nine days, and once patients become ventilated, they frequently require support for 2 weeks.

[figure not shown]
[figure not shown]
It is of interest that the natural history of COVID-19 frequently exhibits a biphasic illness seen with other acute viral and atypical infection. The first part of the illness is driven by direct viral

[figure not shown]
replication in permissive host tissues, which for COVID-19 is largely the respiratory tract. The host immune response to the primary infection results in a second phase, more catastrophic than the first, driven by immune system hyperactivity, often referred to as a ‘cytokine storm.’ Therefore, the successful treatment of more severe infection will likely rely more on immunomodulation rather than on antiviral therapy.¹ IVIG is an immunomodulatory agent used to treat the immunological complications of many infections, including immune-mediated encephalitis and Guillan-Barre.²

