5. A urine or blood pregnancy test will be ordered using urine or blood previously collected for routine care for subjects of childbearing potential who have passed all the other screening criteria and signed consent. If no leftover urine or blood is available, the patient will be asked to take a urine pregnancy test. If the patient already had a pregnancy test during their hospitalization, the results will be extracted from the EMR and used to determine eligibility.
6. The designated research team member will randomize the subject. The randomization will be computer generated using this website in a block of 10. (<https://www.sealedenvelope.com/simple-randomiser/v1/lists>).
7. If the subject is randomized to the “study arm”, then the Research Pharmacy will enter in the order for the IVIG and will not charge the subject. If the subject is randomized to the SOC arm, there is no additional work to be completed by the Research Pharmacy.
8. There are 3 endpoints for this study: discharge to home, receipt of mechanical ventilation, or death. Once one of these endpoints is reached, the subject’s participation in the study will end. As such, the subject may be a candidate for enrollment in another research protocol where appropriate.

Dose: IVIG (Octagam) 0.5g/kg IVPB actual body weight daily x 3 days, with premedication methylprednisolone 40 mg IV push x 1 30-50 minutes before each IVIG infusion.

- Initial infusion rate of IVIG (Octagam) will be of **0.6 mL/kg/hour**, increasing to a maximum rate of 100ml/hr, if tolerated. This is consistent with the standard of care for IVIG at Sharp HealthCare.

Procedure Classification: Aside from a urine or blood pregnancy test for subjects of childbearing potential, there are no other extra tests, imaging scans or procedures that will be performed as part of the study.

Potential Hazards and Precautions: Potential hazards to subjects are described in the “Potential Risks” section, and precautions for subjects are described in the “Protection Against Risks” section.

Research team members will take precautions to minimize exposure to COVID-19 infection by obtaining informed consent electronically, and by collecting data from routine clinical tests as opposed to conducting protocol-specific tests.

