Study Timeframe: The study time frame would be from IRB approval date to the end of the pandemic or until our sites reach 40 subjects, whatever comes first. We anticipate that at the current COVID-19 rate, it should take about 6 weeks to enroll all patients from the time of study initiation.

The end of study for each individual subject will be the date of discharge from the Sharp HealthCare hospital. The subject will not be followed if there is a transfer to a non-Sharp hospital or any sub-acute care setting (i.e., SNF, LTAC, rehabilitation center). A subject's participation will also end if the subject's goals of care have transitioned to palliation, including changing the code status to Do Not Resuscitate or Do Not Intubate of which would render the patient no longer a candidate for intubation.

Method of Subject Identification and Recruitment: The PI or Sub-I will be notified of a COVID-19 confirmed positive patient via hospital generated alert as part of the Infectious Disease Team at each hospital.

Subject Capacity: Subjects who are cognitively impaired or lack the capacity to provide informed consent (as described in HRP-013 section 5.2) may be enrolled in the study if they have an appropriate LAR to provide written informed consent on their behalf. The researchers will follow the guidance outlined in HRP-013 "Legally Authorized Representatives (Surrogate Consent)" when obtaining surrogate consent.

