Subject/Representative Comprehension: Subjects/LARs must have the ability to understand the requirements of the study, provide informed consent, and provide authorization of use and disclosure of personal health information. Subjects with impaired cognitive or decision-making capacity (determined by the PI or designee's assessment of the subject's ability to understand and express a reasoned choice, according to HRP-013 section 5.2.1) must have an appropriate LAR to provide consent on their behalf. If the research subject lacks capacity to consent, the investigator will describe the research to the subject in a manner consistent with the standard consent process and indicate the intent to obtain surrogate consent. This communication will be documented in the research record. If the research subject is non-responsive, the investigator will document this observation in the research record and a note in the subject's medical record that references the research record. If the research subject expresses resistance or dissent to being in the research or to the use of the surrogate consent by word or gesture, she/he will be excluded from the research study.

Documentation of Consent/Assent: Consenting will be conducted as described above in the Procedures and Study Visits section. Consents will be printed and stored in the subject's research binder in a secure location.

Reimbursements or Payments: None

Costs to the Subject: None

Data Sources: Sharp HealthCare electronic medical records (EMR) for hospital in-patients who meet inclusion criteria at acute care facilities.

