Data Collection/ Assessment Instruments: The Case Report Form will include the following data elements: Demographics (age, gender, race/ethnicity, insurance), medical status (pre-existing comorbid conditions (based on the Charlson Comorbidity Index), ferritin level (results will only be collected if lab is ordered as part of the subject's standard of care), CRP level. The tool used to calculate the Charlson Comorbidity Index can be found here <https://www.mdcalc.com/charlson-comorbidity-index-cci#next-steps>). Other data to be collected from standard of care procedures includes vital signs, result of blood or urine pregnancy test, serum creatinine, calculated creatinine clearance (Cockcroft and Gault equation), white blood cell count, platelet count, maximum body temperature in the past 24 hours and oxygen demand rate, whether or not there is an admission to the ICU, any concomitant antimicrobials including azithromycin, doxycycline, hydroxychloroquine, chloroquine, and remdesivir. Receipt of interventions will include standard of care in those who have tested positive for COVID-19. Measures of healthcare service utilization will include length of stay, number of days in ICU, number of days requiring oxygenation, discharge disposition and mortality.

Data Collection Resources: The Study Coordinator will complete the Case Report Forms, with assistance from Sharp's Clinical Analytics team to extract information from the EMR.

Data Analysis: Descriptive statistics will be conducted to describe frequencies of demographics and clinical characteristics including the following: age at discharge, gender, race/ethnicity, payer, comorbid conditions based on the Charlson Comorbidity Index, receipt of medical interventions (mechanical ventilation, medications) and healthcare service utilization (ICU admission and Length of Stay in the hospital). Frequencies and descriptive statistics will be conducted using chi-square or 2-tailed Fisher exact statistics depending on the final sample size for categorical data and t-tests for continuous data. Kaplan-Meier analysis will be performed with assistance from a biostatistician regarding the endpoints of mechanical ventilation and discharge to home endpoints. We do not anticipate number of patient deaths for be sufficient for a meaningful analysis.

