Potential Benefits (Value) to Society: Any data collected will be a benefit to society whether we prove or disprove the hypothesis. However, if it is determined that the studied intervention indeed does reduce demand for mechanical ventilation and ICU care, it may provide significant relief to a medical care system that is anticipated to be overwhelmed at pandemic peak. The benefits will most likely be realized in the next SARS-CoV-2 epidemic. There are potential benefits to each institution that participates in this study to reduce the demand of mechanical ventilation and reduce the demand for isolated negative pressure ICU rooms.

Risk Category: Greater than minimal risk

Potential Risks: All of the adverse reaction and hypersensitivities are detailed in the package insert. These risks are also explained in layman's terms in the Informed Consent Form. The most common adverse reactions include the following: Headaches, allergic reaction and anaphylaxis, aseptic meningitis, venous thrombosis.

Protection Against Risks:

1. Pre-medicate with methylprednisolone IV to reduce/avoid infusion related reactions, including headache, aseptic meningitis.
2. The subject will be in the in-patient acute care setting with the Standard of Care monitoring as would be done if the drug were to be administered outside of the study setting.
3. If the subject experiences side effects that are suspected to be due to the IVIG for subjects in the study group, it will be up to the discretion of the treating clinician/PI whether to continue the IVIG or not.
4. There are no adequate and well-controlled studies of methylprednisolone in pregnant women, and it is not known whether Octagam 10% can cause fetal harm when administered to a pregnant woman or can affect reproduction capacity. Therefore, pregnant women are excluded from participation, and women of childbearing potential will undergo a blood or urine pregnancy test prior to randomization.

Termination of the Study:

1. If the subject prematurely stops study treatment, the study team will continue to collect data until discharge.
2. If the subject progresses into mechanical ventilation, those who are actively receiving IVIG will be stopped.
3. If there are additional doses schedule per protocol and the subject has progressed into the intensive care unit, the additional doses will not be administered.
4. The patient retain the right to terminate the study drug for any reason.
5. Discharge to home

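### Oxygen days, the first secondary outcome, are an undefined inpatient count that stops at discharge, ventilation, death, transfer or palliation, yet would be compared as if complete

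*Combined protocol and SAP*

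**What the plan says.** Secondary Objectives, item 1: "To identify whether adding IVIG to the standard of care will reduce days requiring oxygen therapy". The wording is not limited to days in hospital. Total hospital days are a separate item 2.

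The Data Collection/Assessment Instruments section lists, among measures of service utilization, "number of days requiring oxygenation, discharge disposition and mortality". It gives no start point, stop point or rule for patients still on oxygen when observation ends. The same section lists oxygen demand rate among the data taken from routine care, without saying when it is recorded. Under Data Sources, the source is "Sharp HealthCare electronic medical records (EMR) for hospital in-patients who meet inclusion criteria at acute care facilities".

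Several rules end observation:
- Procedures and Study Visits, item 8: "There are 3 endpoints for this study: discharge to home, receipt of mechanical ventilation, or death". Participation ends once one of these is reached.
- Study Timeframe: "The end of study for each individual subject will be the date of discharge from the Sharp HealthCare hospital".
- Study Timeframe, on transfers: "The subject will not be followed if there is a transfer to a non-Sharp hospital or any sub-acute care setting". The same section ends participation on a move to palliation, including a change to DNR or DNI status. Termination of the Study repeats this.
- Termination of the Study, after early stopping of treatment: "the study team will continue to collect data until discharge".

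That list also contains "Discharge to home" with no condition about oxygen. The Data Analysis section does not name oxygen days. Its general rule for continuous data is the t-test, and Kaplan-Meier analysis is planned only for mechanical ventilation and discharge home.

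**The concern.** Every patient enters on at least 4 L/min of oxygen, so the date on which oxygen stops matters for all of them. The count stops when observation stops, whether or not the patient has come off oxygen. A low count can therefore mean quick recovery, discharge home still on oxygen, early intubation, early death, or transfer. A t-test on the raw count cannot tell these apart.

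The error can run either way. If one arm is discharged earlier while still on oxygen, that arm appears to need less oxygen. If IVIG gets more patients off oxygen before they leave, the remaining need in the control arm is cut off at discharge and the benefit is hidden. The same holds for ventilation, the event the primary objective targets: the arm with more early intubations gains short oxygen counts. For patients still on oxygen at discharge, oxygen days cannot exceed hospital days, so item 1 partly repeats item 2.

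**Working it through.** The documents give no figure for oxygen days, for the share of patients discharged on oxygen, or for oxygen use at home, so there is no figure of the plan's own to reproduce. The check has two parts: tracing what the count can capture, and showing how the error scales under assumed values.

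**What the count captures**

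| How observation ends | Where stated | Still needing oxygen? | Rule for the oxygen count |
|---|---|---|---|
| Discharge home | Procedures, item 8; Study Timeframe; Termination | Possible; no off-oxygen condition | None |
| Mechanical ventilation | Procedures, item 8 | Yes | None |
| Death | Procedures, item 8; Termination | Possible | None |
| Transfer to a non-Sharp hospital or sub-acute care | Study Timeframe | Possible | None |
| Palliation or DNR/DNI | Study Timeframe; Termination | Possible | None |

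For ventilated patients the plan is also unclear on timing. Procedures, item 8, ends participation at ventilation, while Study Timeframe puts the end of study at discharge. Neither says whether ventilator days count as oxygen days.

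Example with assumed figures: two patients go home on day 8. One came off oxygen that day; the other needs 14 more days at home. Both have a count of 8. Their actual oxygen days are 8 and 8 + 14 = 22.

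**Size of the error for discharge on oxygen**

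Let f be the share of an arm discharged on oxygen and d the mean further oxygen days among them. The arm's mean is undercounted by f × d. The error in the difference (SOC minus IVIG) is

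f(SOC) × d(SOC) − f(IVIG) × d(IVIG),

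which reduces to (difference in share) × d when d is equal in both arms. All inputs below are assumptions. At 20 patients per arm, differences of 0.10 and 0.20 are 2 and 4 patients.

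| Difference in share | d = 7 | d = 14 | d = 21 |
|---|---|---|---|
| 0 | 0 | 0 | 0 |
| 0.10 | 0.7 | 1.4 | 2.1 |
| 0.20 | 1.4 | 2.8 | 4.2 |

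Direction:
- 10% (IVIG) v 30% (SOC), d = 14: (0.30 − 0.10) × 14 = 2.8 days of IVIG benefit not seen.
- 30% (IVIG) v 20% (SOC), d = 14: (0.20 − 0.30) × 14 = −1.4, a false IVIG benefit of 1.4 days.

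**Same arithmetic for ventilation**

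The Background says ventilated patients frequently need support for 2 weeks. If ventilator days count as oxygen therapy and the count stops at intubation, a difference of 0.10 in the share ventilated leaves out about 0.10 × 14 = 1.4 days, and 0.20 leaves out 0.20 × 14 = 2.8 days. This applies only on that reading of the variable.

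**The case against.** The strongest reply is that inpatient oxygen days were meant all along. The variable is listed under service utilization beside length of stay and ICU days, it comes from an inpatient record, and the protocol's rationale is relief of hospital resources. On that reading, oxygen at home lies outside the measure and one added word would settle the discharge question. This is a fair reading, but the objective itself carries no such limit. It would also leave the cut-off at ventilation, death, transfer and palliation, all of which shorten inpatient counts too.

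Second, the plan states no scoring rule. A reader might infer that a patient sent home on oxygen is explicitly scored as having finished oxygen therapy, and that the objective is therefore shown to be mis-measured. The documents do not support that. They show an undefined variable and a default test that would treat the count as complete if followed as written.

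Third, the magnitude rests wholly on assumptions. If the share discharged on oxygen and the later duration are equal in the two arms, the difference between arms is unbiased, although both means are too low. This stands.

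Fourth, oxygen demand rate and discharge disposition are already collected. Neither is specified as oxygen status at discharge or tied to the day count, so the gap remains, but the missing item may be available without new collection.

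**Conclusion.** The point holds as a gap in definition and analysis. The plan's only oxygen measure is cut off by five kinds of event, has no rule for any of them, and falls by default to a test that ignores the cut-off. The objective as worded claims more than the data can show.

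Whether the arm comparison is actually biased, and by how much, cannot be known from the documents. Bias requires the terminating events, or the oxygen time remaining after them, to differ by arm. Open-label treatment makes that possible; nothing in the plan shows that it will happen. For discharge on oxygen, the error is 0.7 to 4.2 days under the assumed share differences of 0.10 to 0.20 and 7 to 21 further days, in either direction, and zero if shares and durations are equal. A reader might take one of these figures as the expected bias; they are illustrations only.

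This affects a secondary objective in a 40-patient trial. It is worth correcting because the correction is cheap and changes what the objective can conclude. The conclusion rests on the text available; the part between the Background and the inclusion criteria was not.

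**What to change.** 1. Record oxygen status (yes/no) and flow rate at discharge from the EMR, and report the proportion discharged on oxygen by arm. Since oxygen demand rate is already listed, this may only need a stated time point.
2. For objective 1, analyse time from randomisation to coming off supplemental oxygen within the observed stay, for example as cumulative incidence by arm. Count discharge on oxygen as not liberated. Do not simply censor at discharge, because patients who leave differ from those who stay. Treat ventilation and death as competing events without liberation. State in advance a rule for transfer and for palliation or DNR/DNI.
3. Keep the day count as a descriptive figure, labelled inpatient oxygen days. Define its start and stop, and say whether ventilator days are included.
4. Restrict the conclusion for objective 1 to oxygen use during the observed stay.

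The cost is about one case report form field, a replacement for the t-test on this outcome, and a summary less simple than a mean number of days. No discharge decision or other patient care changes. The fix does not recover oxygen days after discharge; measuring those would need follow-up that the plan does not have.

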1. Confirmed COVID-19 positive test result (including presumptive positive).
2. Hospitalization
3. Requiring ≥ 4 liters/min O_2 nasal cannula to maintain oxygen saturation $\geq 92\%$, but not mechanically ventilated
4. Age ≥ 18 years old.
5. Access to a phone in the hospital room or an electronic device that is capable of receiving phone calls and/or video calls and/or e-mail.
6. Able to read/write/speak English or Spanish fluently.
7. Subjects must have the capacity to provide consent or an appropriate Legally Authorized Representative (LAR) to provide informed consent.
8. Negative pregnancy test for women of childbearing potential.

Exclusion Criteria:

1. Severe allergy to any IVIG product formulation
2. History of DVT, PE, thromboembolic stroke or other thrombotic events

3. Hypersensitivity to corn. Octagam® contains maltose which is a sugar derived from corn.
4. Uncontrolled hypertension (SBP>180 mm Hg or DBP>120mmHg)
5. Active participant in another research treatment study
6. Mechanically ventilated patient
7. Code status is Do Not Resuscitate or Do Not Intubate

Age of Subjects: ≥18 years of age

Gender of Subjects: Either male or female

Racial and Ethnic Origin: Non-specific

Vulnerable Subjects: Hospitalized subjects

Study Design: Investigator initiated, open label, multicenter, two arm, randomized study to compare the impact of adding IVIG to the Standard of Care (SOC) to the SOC without IVIG. Randomization ratio will be 1:1.

Procedures and Study Visits:

1. The PI will be notified of a COVID-19 tested positive patient via hospital generated alert.
2. The PI or designee will prescreen the patient using the inclusion and exclusion criteria.
3. PI or Sub-I will contact the study team, if the patient passes prescreening.
4. The CRC will obtain an informed consent from the subject or LAR either electronically utilizing DocuSign® or with a paper copy utilizing an impartial witness:
 - a. The research team will utilize DocuSign® for the signing of the consents in order to be compliant with the infection control measures taken place for Highly Infectious Diseases. Below are the steps of the DocuSign® procedure:

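### Hospital days as worded run from admission, and oxygen days have no stated start, so both secondary outcomes can include days fixed before randomisation; both should be counted from randomisation

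*Combined protocol and SAP*

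**What the plan says.** The Secondary Objectives of the combined protocol and SAP are "To identify whether adding IVIG to the standard of care will reduce days requiring oxygen therapy" and "To identify whether adding IVIG to the standard of care will reduce total hospital days". Neither gives a day on which counting starts.

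The section on data collection lists the matching data elements: "Measures of healthcare service utilization will include length of stay, number of days in ICU, number of days requiring oxygenation, discharge disposition and mortality". The Data Analysis section names the hospital variable within "healthcare service utilization (ICU admission and Length of Stay in the hospital" and plans "t-tests for continuous data", with no covariate adjustment. It does not name oxygen days, which would fall under the same t-test rule. It also plans Kaplan-Meier analysis of mechanical ventilation and of discharge home, without a time origin.

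Inclusion item 2 requires hospitalisation, and item 3 begins "Requiring ≥ 4 liters/min O_2 nasal cannula to maintain oxygen saturation". Randomisation follows prescreening, consent and, where applicable, a pregnancy test (Procedures and Study Visits, items 2 to 6). Neither the eligibility lists nor the procedures limit the time from admission, or from the start of oxygen, to randomisation.

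The total is 40 patients (Study Timeframe), 20 per arm (Data Monitoring).

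**The concern.** IVIG can act only after allocation. Hospital days and oxygen days before randomisation are already settled, so including them adds a component that treatment cannot change. Every patient has some such time, because hospitalisation and an oxygen need come before consent and randomisation. Its length can vary between patients, because nothing caps it.

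Two things are at stake. First, a percentage reduction in total stay understates the percentage reduction in the part that IVIG could shorten. Second, variation in the earlier days may widen the standard error of a comparison that has only 20 patients per arm. The planned tables would not show whether the arms differed in this respect, since neither days from admission to randomisation nor prior oxygen days is among the listed case report form items or descriptive variables.

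**Working it through.** **The plan's own figure.** The sample size of 40 is given without alpha, power, effect size or SD, so it cannot be reproduced. Assuming two-sided alpha 0.05 and 80% power, 20 per arm detects a difference of (1.960 + 0.842) × √(2/20) = 0.886 SD.

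**Inputs.** From the documents: 20 per arm, 1:1 allocation, unadjusted t-test. Assumed, because the documents give no figures: SD of post-randomisation days s = 7; SD of pre-randomisation days p = 1, 2, 3 or 4; correlation ρ between the two = 0, then -0.3 and +0.3.

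**Formulas.** Variance of total days = s² + p² + 2ρsp. SE of the difference in means = √(variance × 2/20). Equivalent patients = 40 × s² / variance.

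**Independent case (ρ = 0).**

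| p (days) | Variance | Increase over 49 | SE (days) | Equivalent patients |
|---|---|---|---|---|
| 0 (counted from randomisation) | 49 | none | 2.21 | 40 |
| 1 | 50 | 2% | 2.24 | 39 |
| 2 | 53 | 8% | 2.30 | 37 |
| 3 | 58 | 18% | 2.41 | 34 |
| 4 | 65 | 33% | 2.55 | 30 |

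**Correlation.** For p = 2, 3, 4:

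- At ρ = +0.3 the variance is 61.4, 70.6, 81.8, a rise of 25%, 44%, 67%.
- At ρ = -0.3 it is 44.6, 45.4, 48.2, or 0.91, 0.93, 0.98 of the post-randomisation variance, so nothing is lost.
- The loss vanishes where p² + 2ρsp = 0, that is at ρ = -p/(2s) = -0.14, -0.21, -0.29.

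**Power.** Take the difference that has 80% power when counted from randomisation. If p/s = 0.5, power counted from admission is 70.7% at ρ = 0, 61.4% at ρ = +0.3 and 82.0% at ρ = -0.3.

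**Relative effect.** A true 30% cut in an assumed 10-day post-randomisation stay is 3 days. As a share of total stay it is 3/(10 + days before randomisation): 27.3%, 25.0%, 23.1% or 20.0% for 1, 2, 3 or 5 earlier days.

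**Bias.** Allocation cannot affect earlier days, so their expected difference between arms is zero. In a simulation of 20,000 trials with 20 per arm, a true difference of -2 days in total stay was recovered as -2.02.

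**The case against.** No section states that counting starts at admission. That is the ordinary meaning of total hospital days and length of stay, not a written definition. For oxygen days and the Kaplan-Meier curves the start is simply absent. This stands, and the point is worded accordingly. The text between the Background and the inclusion list was not available for this review; a definition there would settle the matter.

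Total stay is also a coherent measure of resource use. The protocol lists it under utilisation and presents the benefit partly as relief of demand on the health system. Under randomisation its absolute difference is unbiased. This stands too, and is a reason to keep total stay as a descriptive measure.

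The size of the loss, and even whether there is one, rests on an SD and a correlation that the documents do not give. The calculation shows as much.

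A reader might go further and infer that chance imbalance in the earlier days could pass for a treatment effect. Taken alone, those days would differ between arms by at least 1 day in 11%, 29% or 43% of trials for SDs of 2, 3 or 4. The documents do not support that inference, for three reasons:

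- They state no target effect for either secondary outcome.
- The t-test's standard error already contains this variation, so its error rate is kept.
- With a post-randomisation SD of 7, a gap of at least 1 day with no treatment effect occurs in about 65% of trials anyway, and in 66%, 68% or 69% with the earlier days added.

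Nor can one conclude that the Kaplan-Meier curves contain time in which no enrolled patient could have been ventilated. That would follow only from an admission origin, and none is stated.

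**Conclusion.** The point holds as a matter of outcome definition. Followed literally, the plan puts days fixed before allocation into the hospital-days outcome, and it leaves oxygen days open to the same reading. The consequences are a diluted relative effect and, in most of the scenarios shown, some loss of precision. There is no systematic bias in the absolute difference and no inflation of false positives.

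With the assumed SD of 7 days after randomisation and independent SDs of 2 to 4 days before it, the SE rises from 2.21 to between 2.30 and 2.55 days, an increase of 4% to 15%. The loss is negligible at an SD of 1 day. These are secondary outcomes and the harm is bounded, but with 40 patients and so cheap a remedy the change should be made.

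**What to change.** Define hospital days as days from randomisation to discharge, and oxygen days as days on oxygen from randomisation onward. State that both Kaplan-Meier curves start at randomisation. Record the randomisation date, and report hospital days and oxygen days before it by arm as baseline characteristics. Keep total length of stay as a descriptive utilisation measure.

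The cost is protocol wording plus small case report form additions. The form now lists a number of oxygen days rather than dated oxygen use and names no randomisation date, so admission, randomisation and oxygen start and stop dates need fields. They should be retrievable from the electronic medical record and study records. No new test or visit is needed. If randomisation was already the intended origin, one sentence in the protocol settles it.
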